4.0 Study Endpoints

- The primary outcome will be postoperative cumulative opioid consumption (in IV morphine mg equivalents: IV MME) over time, up to 72 hours postoperatively. Cumulative opioid consumption will be evaluated at in PACU, and through 72 hours post-op.
- Secondary outcomes: Postoperative pain score measures on the visual analog scale (VAS) captured in the preoperative area, PACU, and through 72-hours post-op.
- Additional outcomes of interest include time to first ambulation, functional and mobility outcomes, PACU duration, patient satisfaction, and opioid related side effects.

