10.0 Study Design / Methods

- **Objective and outcomes:** Determine if PENG+LFC blocks reduce opioid consumption compared to a QL block after THA.
- **Design:** This prospective, blinded clinical trial will randomize subject to receive a PENG+LFC or QL block prior to THA. The randomization will be created by a statistician prior to subject enrollment.
- **Groups:** Subjects will be randomized to receive a preoperative PENG+LFC (n=53) or QL (n = 53) block prior to THA.
- Potential participants that are on the operating room schedule for THA will be screened for eligibility via chart review.

Baseline

- Once subjects have signed an informed consent, they will be assigned an enrollment number. Randomization will be created prior to the study starting with half of the research subject numbers being assigned to receive a PENG+LFC block, and the other half assigned to receive a QL block. Both blocks are considered our current standard of care. A study team member will open the envelope labeled with the subject's assigned study ID to reveal the randomization assignment.

- The participant's medical record will be reviewed for demographic data collection and durations (operative, PACU, hospital stay).
- Before placing the block, participants will be asked what their current pain score is by using a Visual Analog Scale (VAS) from 0-100, and complete the HOOS Jr, and PROMIS-10 Global Health questionnaires.

Randomization

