The participant will be asked to provide their average pain score while at rest, and average pain score with movement in the specified time period using a visual analog scale from 0-100 with 100 being the worst. The first pain score will be recorded before they leave the PACU on the day of the procedure. Beginning the following morning, the participant will receive a text message link sent by Twilio's secure server that opens a survey housed in RedCap. The first text message will arrive at 9:00 AM and will follow the schedule in **Table 1**.

The follow-up text messages will also ask the patient the name, dose, and frequency of any pain medication taken in that time period. On Day 7, the text message survey will assess functional outcomes by using two different questionnaires. The patient will schedule at least two post-operative in-person follow up visits as standard of care. One visit at approximately 2-3 weeks post-op, and the other at approximately 6 weeks.

During these two visits the patient will complete the same functional questionnaires as they did at Baseline and on Day 7. This may be done in person at their standard of care post-op visits or may be contacted by study personnel to complete via telephone. Adverse events will also be collected throughout the study.

The text messages are sent from a secure server, Twilio, and are housed in REDCap. The set of questions will state what time window (example: 12:00 AM midnight the night prior to 12:00 PM noon the same day) to consider when answering the questions.

If the participant has been discharged from the hospital, they will answer these questions in the text message each day. If they are admitted to the hospital at these points in time, the information will be gathered from their chart for medications and asked verbally for pain scores and additional questions. Additional data will be recorded by physical therapy and surgical staff and pulled from the patient's medical record for data collection.

If the participant is unable or unwilling to receive text messages, they will be provided a paper document to record their data for the pre-determined intervals so when a study member contacts them, they are able to relay their answers back accurately.

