Care in the perioperative period will otherwise be standardized. In the post-anesthesia care unit (PACU), hydromorphone or morphine will be titrated by the PACU nurse for the subject's comfort. Additionally, as standard of care, Physical Therapy will evaluate patients in the PACU before discharge.

An outline of study time points and assessments is shown in **Table 2**.

Table 1. Post-Op Follow Up Assessment Schedule

Post-Op Day	Time of Text Message	Data Collection Time Period
POD 0	Right before discharge	Waking up from surgery to discharge
POD 1-AM	9:00 AM	Discharge to 11:59 midnight prior
POD 1-PM	3:00 PM	12:00 AM midnight night prior to 12:00 PM noon same day
POD 2-AM	9:00 AM	12:01 PM noon day prior to 11:59 PM midnight night prior
POD 2-PM	3:00 PM	12:00 AM midnight prior to 12:00 PM noon same day
POD 3-AM	9:00 AM	12:01 PM noon day prior to 11:59 PM midnight night prior
POD 3-PM	3:00 PM	12:00 AM midnight prior to 12:00 PM noon same day

Table 2. Summary of Study Procedures and Follow-Ups	
Study Activities	Details/Assessments
Informed consent	
 Obtain informed consent
Baseline	
 Pre-Operative VAS Pain Score Quad Strength Pre-Op HOOS Jr PROMIS-10 Global Health
Randomization (day 0)	
 Confirm eligibility criteria Randomization
Randomization procedure (day 0)	
 Complete PENG or QL Block according to randomization allocation
Post-Op First Opportunity in PACU	
 Opioid Consumption
Ambulation (Assessed by Physical Therapy in PACU)	
 Time that first ambulation occurred in PACU Distance ambulated in PACU Quad Strength in PACU
Post-Op Day 1 9:00 AM (text message)	
 Opioid and pain medication consumption VAS Pain Score
Post-Op Day 1 3:00 PM (text message)	
 Opioid and pain medication consumption VAS Pain Score
Post-Op Day 2 9:00 AM(text message)	
 Opioid and pain medication consumption VAS Pain Score
Post-Op Day 2 3:00 PM (text message)	
 Opioid and pain medication consumption VAS Pain Score
Post-Op Day 3 9:00 AM (text message)	
 Opioid and pain medication consumption VAS Pain Score

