11.0 Data Management

- **Sample size and power:** The primary outcome for assessing differences between PENG+LFC vs. QL blocks will be postoperative cumulative opioid consumption (in IV morphine mg equivalents; IV MME) over time, up to 72 hours postoperatively. Cumulative opioid consumption will be evaluated in PACU, and at 12-hour intervals during the first 72 hours of the postoperative window. Differences in cumulative opioid consumption over time between block groups will be assessed using a linear mixed model approach. The model will include fixed effects for treatment group, postoperative time, and the interaction between block group and postoperative time and a random subject effect to account for correlation between measures collected on the same patient over time. Differences between block types at each postoperative time will be evaluated using linear contrasts from the model. A previous study⁹ conducted at MUSC found mean IV MME at 12 hours postop in subjects undergoing THA with a QL block was 16 ± 12 MME. A sample size of 48 subjects per group with 9 repeated measures of opioid consumption provides 80% power to detect a difference in cumulative MMEs consumed postoperatively of 4 MMEs at significance level $\alpha = 0.006$ (Bonferroni adjusted for 9 pairwise comparisons between group) assuming a standard deviation of ± 12 MMEs, a first-order autoregressive correlation structure and correlation between observations on the same subject of $\rho = 0.33$. We will plan to enroll 53 subjects/group (106 total) to allow for 10% attrition.
- Postoperative VAS pain score captured in the preoperative area, PACU and 12-hour intervals during the first 72 hours of the postoperative window will be collected as a secondary outcome and will be evaluated using a LMM similar to the primary outcome. Additional outcomes of interest include time to first ambulation, functional and mobility outcomes, PACU duration, patient satisfaction, and opioid related side effects.

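### The pre-block VAS is listed among the postoperative pain scores and the pain model names no baseline term; entering it as a covariate is a cheap, modest precision gain for a secondary outcome

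*Combined protocol and SAP*

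**What the plan says.** Two sections place the preoperative score inside the postoperative outcome:

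- Section 11.0 Data Management: "Postoperative VAS pain score captured in the preoperative area, PACU and 12-hour intervals during the first 72 hours of the postoperative window".
- Section 4.0 Study Endpoints: "Postoperative pain score measures on the visual analog scale (VAS) captured in the preoperative area, PACU, and through 72-hours post-op".

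Three places in Section 10.0 treat it as a baseline:

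- The Baseline text: "Before placing the block, participants will be asked what their current pain score is by using a Visual Analog Scale (VAS) from 0-100".
- Table 2, Baseline row: "Pre-Operative VAS Pain Score".
- Post-Op and Follow-Up: "The first pain score will be recorded before they leave the PACU on the day of the procedure". This part also asks for two postoperative ratings, average pain at rest and average pain with movement, each over a stated window.

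On the analysis, Section 11.0 says that the VAS "will be collected as a secondary outcome and will be evaluated using a LMM similar to the primary outcome". The primary model has "fixed effects for treatment group, postoperative time, and the interaction between block group and postoperative time and a random subject effect", with group contrasts at each postoperative time. No section says whether the pre-block score is a response, a covariate, a constrained baseline or descriptive only.

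**The concern.** A score taken before the block cannot be an effect of the block. The primary outcome, postoperative opioid use, has no pre-block value, so a model borrowed from it gives no guidance on how to handle one. Read literally, Sections 4.0 and 11.0 make the pre-block score one more response row. Read with Table 2, it is a baseline whose use is unspecified.

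Precision and clarity are at stake. As a free response row, the score is nearly wasted. As a covariate, it may narrow the pain contrasts. Leaving the role open also lets the choice be made after the data are seen.

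**Working it through.** **The plan's own figure.** No power or correlation is stated for VAS. The primary figure is the only one to reproduce, and it is needed here only for its inputs. The variance factor for the mean of 9 measures under first-order autoregressive, AR(1), correlation 0.33 is [9 + 2 × Σ(9 − k) × 0.33^k] / 81 = 0.2024, so the variance is 144 × 0.2024 = 29.15 (SD 5.40). With two-sided alpha 0.006 (sidedness assumed), n = 2 × (2.748 + 0.842)² × 29.15 / 4² ≈ 47 per group. With alpha 0.05/9, n is 48. The stated 48 reproduces.

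**Inputs for VAS**
- 48 per group, from 53 enrolled: "We will plan to enroll 53 subjects/group (106 total) to allow for 10% attrition" (Section 11.0).
- 7 postoperative times: PACU, then 12 to 72 hours in 12-hour steps (Section 11.0; Table 1 also has 7 windows).
- Baseline-to-postoperative correlation r: not in the documents. Assumed range 0.2 to 0.6. The value 0.33 is borrowed from the opioid outcome.
- SD set to 1, because only ratios matter.

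**Unadjusted, or free response row with complete data.** With categorical time and a full group-by-time interaction, each contrast is the raw difference in means. Its variance is 2/48 (SE 0.2041) with or without the pre-block row, so the ratio is 1.000 at every time. If 5 of 53 per group are lost right after baseline, the free row recovers a little: 1 − r² × 5/53 = 0.996, 0.990 and 0.966 for r = 0.2, 0.33 and 0.6.

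**Baseline covariate with a slope at each time.** The variance ratio, net of estimating the slope, is (1 − r²) × (1 + 1/(96 − 4)) = (1 − r²) × 1.0109.

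| Constant r | Variance ratio | Variance reduction | SE reduction |
|---|---|---|---|
| 0.2 | 0.970 | 3.0% | 1.5% |
| 0.33 | 0.901 | 9.9% | 5.1% |
| 0.6 | 0.647 | 35.3% | 19.6% |

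Simulation with 48 per group (40,000 trials per value) gave 0.963, 0.894 and 0.641, and 1.011 at r = 0. These agree to within about 0.01.

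**AR(1) decay from 0.33**, counting pre-block to PACU as one step: r is 0.33, 0.109, 0.036 and then smaller. The ratios over the 7 times are 0.901, 0.999, 1.010, 1.011, 1.011, 1.011 and 1.011, with mean 0.993. Almost all the gain is at PACU.

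**Cost.** Break-even is r = √(1 − 1/1.0109) = 0.104. At r = 0 the variance rises 1.1% and the SE by √1.0109 = 1.005, or 0.5%.

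**One common slope instead.** In simulation under the same AR(1) decay, the ratios were 0.960 and 0.991 at the first two times, then 1.003 to 1.007. The PACU gain falls from about 10% to about 4%, which favours a slope at each time.

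**Missing baselines.** A standard mixed model drops a subject whose covariate is missing. As an illustration (assumption), two missing per group would multiply variance by 48/46 = 1.043 at every time, more than the 1.1% above.

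**The case against.** The strongest reply is that nothing is invalid. Randomisation makes the unadjusted contrasts unbiased, the outcome is secondary, and adjustment is a matter of efficiency. The documents also narrow the ambiguity: Table 2 files the score under baseline, and the borrowed model refers to postoperative time and postoperative contrasts. Saying that the model will be similar to the primary one does not exclude a baseline term. All of this stands, and it keeps the point minor. It does not settle which analysis will be run, because the two sections that define the outcome still list the score among its measurements.

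The gain may also be small. The only correlation in the documents belongs to opioid use, and under its AR(1) form five of the seven times lose slightly. One rating of current pain, with neither rest nor movement specified, set against windowed averages also points to the lower end of the range. This stands too: adjustment could help, but the documents do not show that a gain is likely at every time.

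A reader might infer that the group effect would be diluted to 7/8 of its postoperative value by averaging over 8 rows, one of them pre-block. The documents do not support that: the planned contrasts are at each postoperative time, and no average over all rows is specified.

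**Conclusion.** The point holds as a minor, inexpensive improvement to a secondary outcome. The documents label the pre-block VAS inconsistently and give it no analysis role. A free response row adds no precision with complete data and little with the planned attrition, and it puts into the model a group difference that the block cannot have caused.

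The size of the gain from adjustment cannot be determined from the documents. Under assumed constant correlations of 0.2 to 0.6 it is about 3% to 35% of contrast variance; under AR(1) decay from 0.33 it is worthwhile at PACU only. The variance figures rest on 48 per group, categorical time, complete baselines and a slope at each time.

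It would be wrong to conclude that the planned pain contrasts are biased, that baseline adjustment has been ruled out, or that the primary analysis or sample size is affected. Nor is the roughly 1% variance loss the only cost: missing baselines need a rule.

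**What to change.** In Section 11.0, state that:

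- the pre-block VAS enters as a fixed baseline covariate with a baseline-by-time interaction, in a separate mixed model for each postoperative VAS outcome (rest and movement), with the same single baseline score in both;
- only PACU through 72-hour scores are response rows;
- subjects with a missing pre-block score are kept by imputing the overall mean, calculated without regard to group.

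An acceptable alternative is to keep the pre-block score as a response row with its mean constrained equal between groups, provided the covariance is modelled suitably. This also keeps subjects with a missing baseline.

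Reword Section 4.0 so that the preoperative score is named as a baseline and not as a postoperative measure.

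The cost is a few sentences. No new data are needed, because the score is already scheduled. With the missing-baseline rule in place, the statistical cost is about 1% of variance (0.5% of SE) at times where the baseline correlation is near zero.

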12.0 Provisions to Monitor the Data to Ensure the Safety of Subjects

- All new complaints and symptoms (i.e., those not existing prior to signing of informed consent) will be recorded on the AE CRF. All AEs will be characterized in terms of their start and stop dates, intensity, action taken, relationship to intervention, subject outcome, and whether or not the AE led to an SAE.
- Any adverse events related to placement of nerve blocks will be treated according to MUSC Hospital policy and procedures and the practice of the Department of Anesthesia.
- The Department of Anesthesia's DSMB will review the study on an annual basis. Any adverse events will be reported and reviewed by the DSMB. Adverse events will be reported to MUSC's IRB per policy.
- All data will be kept in a locked office, in a locked cabinet, and electronic data will be stored on a password protected MUSC server. Only CITI certified, IRB approved study team members will have access to data.

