- All subjects will be positioned, prepped, and sedated for the randomized regional anesthesia procedure in the preoperative holding area. The subject will be positioned in the supine position and pulse oximetry and blood pressure cuff placed for monitoring. As part of routine care, the subject will receive sedation for their comfort. All subjects would receive 30 ml of 0.25% ropivacaine in their nerve block regardless of randomization. The relevant anatomy will then be identified using ultrasound guidance and real time imaging. For both groups, ropivacaine will be injected slowly with frequent aspiration to rule out inadvertent intravascular needle placement. Local anesthetic injection will also be observed with real time ultrasound guidance. All participants, regardless of group assignment, will have subcutaneous numbing medication placed just below the skin at both block sites (skin wheal). This will be done so that participants and the research team collecting results will be blinded. Subjects, surgeons, and data collectors will all be blinded to the allocated group. Unblinded personnel will be the Anesthesia Attending placing the block and clinical staff assisting.
- In subjects randomized to the QL group, ultrasonography will be used to identify external oblique, internal oblique, transverse abdominus, and quadratus lumborum muscles. A needle will then be advanced under ultrasound guidance below the internal oblique aponeurosis and lateral to the quadratus lumborum muscle. Ropivacaine will be injected slowly with frequent aspiration to rule out inadvertent intravascular needle placement. Local anesthetic injection will also be observed with real time ultrasound guidance.
- In subjects randomized to the PENG+LFC group, ultrasonography will be used to identify the anterior inferior iliac spine, iliopsoas tendon, and iliopubic eminence. After placing a subcutaneous skin wheal with lidocaine, a needle will be advanced until the tip lies on the lateral and inferior margin of the iliopsoas tendon between the anterior inferior iliac spine (lateral) and iliopubic eminence (deep).

Post-Op and Follow-Up

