14.0 Risks to Subjects

- PENG+LFC Block: risks include infection, bleeding, local anesthetic systemic toxicity (LAST), nerve damage, block failure, and quadricep weakness. Infection risk is minimized by utilizing appropriate antiseptic and sterile technique as is standard for any regional procedure. The risk of LAST is a risk with any regional procedure and is minimized by frequent aspiration, incremental local anesthetic injection, and vital sign monitoring throughout.
- QL Block: risks include infection, bleeding, local anesthetic systemic toxicity (LAST), nerve damage, block failure, and quadricep weakness. Infection risk is minimized by utilizing appropriate antiseptic and sterile technique as is standard for any regional procedure. The risk of LAST is a risk with any regional procedure and is minimized by frequent aspiration, incremental local anesthetic injection, and vital sign monitoring throughout. There is also a risk of quadricep weakness.
- Subjects will be randomly assigned to receive either 1) PENG + LFC or 2) QL block. One group may prove to be less beneficial than the other.
- There is also a risk of loss of confidentiality.

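### The adverse event recording rule covers new complaints and symptoms but does not require recording a pre-existing symptom or deficit that worsens after the block

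*Combined protocol and SAP*

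**What the plan says.** Section 12.0 sets the recording rule: "All new complaints and symptoms (i.e., those not existing prior to signing of informed consent) will be recorded on the AE CRF". It then lists what is noted about each event: "All AEs will be characterized in terms of their start and stop dates, intensity, action taken, relationship to intervention, subject outcome". The next two bullets of that section refer to events related to placing the block and to oversight: "Any adverse events will be reported and reviewed by the DSMB". Section 10.0 adds a general statement: "Adverse events will also be collected throughout the study". Table 2 names adverse events as an item at the afternoon contact on day 3, at day 7, at weeks 2-3 and at week 6. It shows no such item at the block procedure, in PACU, or on days 1 and 2.

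Section 14.0 lists, for each of the two blocks, risks that include "nerve damage, block failure, and quadricep weakness". Table 2 schedules quadriceps strength twice, at baseline ("Pre-Operative VAS Pain Score Quad Strength Pre-Op HOOS Jr") and after surgery ("Quad Strength in PACU"). No text links a decline between the two readings to the adverse event rule.

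**The concern.** A recording rule normally covers both new events and deterioration of existing ones. Here the test is whether the symptom existed before consent, and a symptom that did exist does not meet it, however much worse it becomes. That matters in a population having hip arthroplasty, where some patients may already have pain, weakness or altered sensation in the limb. Two of the harms the protocol itself expects, nerve damage and quadriceps weakness, can appear as deterioration of such a deficit.

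The second question is whether complaints and symptoms extend to signs that staff find and the patient does not report. It arises because patients are sedated for the block: "As part of routine care, the subject will receive sedation for their comfort".

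At stake is the completeness of the safety record that the DSMB and IRB rely on, and of the harms reported when the trial ends.

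**Working it through.** No arithmetic applies. The check is to set the relevant text side by side and ask whether anything widens the rule.

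1. **Definition of new (section 12.0).** The parenthesis in "All new complaints and symptoms (i.e., those not existing prior to signing of informed consent) will be recorded on the AE CRF" fixes the meaning as not present before consent. Severity and change are not part of the test.
2. **Event attributes (section 12.0).** Intensity is recorded, but only for something already counted as an event. This does not bring a worsened pre-existing symptom into scope.
3. **Other uses of the term.** Section 10.0 ("Adverse events will also be collected throughout the study"), Table 2 and the DSMB bullet ("Any adverse events will be reported and reviewed by the DSMB") use the term without defining it. None mentions worsening.
4. **Could prior deficits be present? (section 5.0).** The four exclusions are local anesthetic allergy, weight under 40 kg, no informed consent, and known preoperative substance abuse. None removes a patient with existing weakness or numbness.
5. **Is the worsening captured elsewhere? (sections 4.0 and 10.0, Table 2).**
   - Pain: VAS before the block, in PACU and through 72 hours. Worsening is visible as outcome data.
   - Weakness: quadriceps strength at baseline and in PACU. Early worsening is visible. No later strength reading is scheduled, so later change could show only indirectly through HOOS Jr and PROMIS-10 at day 7, weeks 2-3 and week 6.
   - Numbness: no sensory assessment is listed at baseline or follow-up. Worsening has no other route into the data.
   - In each case an outcome value lacks the relationship, action taken and outcome fields that an adverse event entry carries.
6. **Signs seen by staff.** The rule speaks of complaints and symptoms, which most naturally means what patients report. Section 10.0 says physical therapy and surgical staff record additional data and that data are drawn from the chart, but does not name these as a source of adverse events. Against that, section 12.0 refers to events related to block placement, and these are often first seen by the clinician.

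Steps 1 to 4 establish the gap on worsening. Step 5 narrows its practical effect. Step 6 leaves an ambiguity rather than an exclusion.

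**The case against.** The strongest reply is that the rule sets a minimum. It does not say that nothing else may be recorded, and the same section speaks of any adverse events going to the DSMB. Events of block placement, such as local anesthetic toxicity or bleeding, arise after consent and so are new by definition. It would be strange to read section 12.0 as leaving them out when it provides for them. This largely answers the point about staff-observed signs; what remains is that the wording is narrow and Table 2 has no adverse event item before day 3. It does not answer the point about worsening, because nothing in the documents requires that to be recorded.

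It is also fair to say that worsened pain and early weakness remain visible as outcomes. That stands, and it limits the consequence.

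A reader might infer more than the text supports:

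- **That the loss would differ between arms and make safety look falsely balanced.** Section 3.0 does describe some block-specific risks. But the rule is the same in both arms, section 14.0 lists nerve damage and quadriceps weakness for both, and no between-arm comparison of adverse events is planned. Differential loss is not shown.
- **That a given number of the 106 patients would be affected.** The documents give no frequency of prior deficits. A count of patients with a prior symptom would in any case not be a count of missed events: a patient with prior weakness who develops numbness for the first time still has a new symptom.
- **That DSMB and IRB reports are compiled solely from this form.** Section 12.0 does not say so; reporting to the IRB follows a policy that the documents do not reproduce.

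**Conclusion.** The point holds in a limited form. The only stated criterion for the adverse event form does not require recording a pre-existing symptom or deficit that worsens after the block. The gap is clearest for numbness, which has no other measure, and for weakness after PACU, where no further strength reading is scheduled. Whether staff-observed signs are covered is unclear from the wording, although the surrounding text suggests that they are intended.

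The effect is a possibly incomplete safety record. Its size cannot be estimated from the documents. It does not touch the opioid consumption analysis. The conclusion assumes that site staff follow the rule as written; staff who apply a broader understanding of an adverse event would lose less. This is a cheap improvement.

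**What to change.** Reword the first sentence of section 12.0 along these lines: *Any untoward sign, symptom or clinically relevant finding that is new, or that has worsened from the pre-block baseline, whether reported by the subject or observed by staff, is to be entered on the AE CRF.*

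Add a CRF instruction that events of the block procedure are entered on day 0. The anesthesia attending and assisting staff are unblinded while data collectors are blinded (section 10.0), so the entry route should not reveal the allocation, for example by keeping these entries out of the data collectors' view until follow-up is complete.

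No automatic rule turning a fall in quadriceps strength into an adverse event is needed to close the gap; strength can remain an outcome measure.

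The cost is one sentence, one CRF instruction and somewhat more entries. No new assessment is required. Because sensation is not measured at baseline, worsening numbness would be judged from the patient's account or the chart. The change is best made prospectively, since events not recorded at the time may not be recoverable.
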